These amendment items are considered to contribute to improve readability and accessibility of the protocol.

Changes to the protocol

Changes to specific sections of the protocol are shown in the track changes version of the protocol using red underlined font for insertions. This amendment is considered substantial.

The following sections, tables and figures were changed:

- [Section 1.1](#): inclusion of information concerning FDA approval of asciminib for adult patients with Ph+ CML -CP, previously treated with two or more TKIs. The recommended dose of asciminib is a total daily dose of 80 mg, taken either as 80 mg q.d. or 40 mg BID. The FDA also approved asciminib for adult patients with Ph+ CML in CP with T315I mutation. The recommended dose of asciminib in patients with Ph+ CML in CP with T315I mutation is 200 mg BID.
- [Section 2.1](#): updated wording on investigational treatment
- [Section 4.2](#): clarification regarding blood pressure assessment in supine position only
- [Figure 4-1](#): dose of “40 mg” is specified in the title
- [Section 5.2](#): addition of an exclusion criterion for recent participation in an interventional trial and clarify the IMP wash-out period required for study participation

- [Section 5.2](#): removal of exclusion criteria regarding ‘history of active ongoing acute or chronic liver disease’ as it was not in sync with inclusion of patients having baseline moderate hepatic impairment (total bilirubin $\leq 3 \times$ ULN)
- [Section 5.2](#): clarification regarding baseline evaluation of Hepatitis B parameters are added. HBV DNA estimations are required only if anti-Hbc is positive. Patients having HbsAg positivity will automatically be excluded, and HBV DNA estimations are not required in such scenario.
- [Section 5.2](#): statement added to contraception criteria based on FDA request regarding female contraception
- [Table 6-4](#): dose withholding guidelines were updated for patients who experience 5- to 20-fold ULN transaminase elevations while taking asciminib. In addition, appropriate dose modifications guidelines in patients having elevated transaminase levels at baseline are added. This change has been implemented in the protocol in response to the MHRA comment to revise the current dosing recommendations for transaminase elevations of 5- to 20-fold ULN in the protocol.

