Investigations (hematologic): If a hematologic toxicity (cytopenia grade 3 or 4) lasts for more than 42 days without recovery to at least grade 2, despite asciminib interruption and adequate management (including hematopoietic growth factors), then the patient should be discontinued from study treatment.	
Neutropenia (ANC)	
Grade 1 (ANC < LLN – 1.5 x 10 ⁹ /L)	Recommendation: Maintain dose level
Grade 2 (ANC < 1.5 – 1.0 x 10 ⁹ /L)	Recommendation: Maintain dose level
Grade 3 (ANC < 1.0 – 0.5 x 10 ⁹ /L)	Mandatory: Hold dose until resolved to grade ≤ 2 (recheck CBC 2x/week), then: if resolved in ≤ 14 days, then maintain dose level If resolved in > 14 days, then reduce dose ↓ 1 dose level
Grade 4 (ANC < 0.5 x 10 ⁹ /L)	Mandatory: Hold dose until resolved to grade ≤ 2, (recheck CBC 2x/week), then: if resolved in ≤ 14 days, then maintain dose level if resolved in > 14 days, then reduce dose ↓ 1 dose level

Dose modifications for asciminib	
Please note that if a patient requires a dose interruption of > 28 days for any toxicity, and > 42 days for hematologic toxicity, then the patient should be discontinued from study treatment	
Worst toxicity CTCAE Version 5.0	Asciminib
Febrile neutropenia (ANC < 1.0 x 10 ⁹ /L, fever ≥ 38.5°C)	Mandatory: Hold dose until resolved, then reduce dose ↓ 1 dose level
Thrombocytopenia	
Grade 1 (PLT < LLN – 75 X 10 ⁹ /L)	Recommendation: Maintain dose level
Grade 2 (PLT < 75 - 50 x 10 ⁹ /L)	Recommendation: Maintain dose level
Grade 3 (PLT < 50 - 25 x 10 ⁹ /L)	Mandatory: Hold dose until resolved to grade ≤ 2 (recheck CBC 2x/week), then: if resolved in ≤ 14 days, then maintain dose level if resolved in > 14 days, then reduce dose ↓ 1 dose level
Grade 4 (PLT < 25 x 10 ⁹ /L)	Mandatory: Hold dose until resolved to grade ≤ 2 (recheck CBC 2x/week), then: if resolved in ≤ 14 days, then maintain dose level if resolved in > 14 days, then reduce dose ↓ 1 dose level
Recurrence of any cytopenia	Recommendation: Hold dose until resolved to grade ≤ 2, then maintain current dose level For recurrent Grade 3/4 cytopenia, please refer to above guidelines for neutropenia and thrombocytopenia; no further dose reduction is allowed for already reduced dose.
Non-hematologic adverse reactions except where further specified in individual sections	
Grade 1	Recommendation: Maintain dose level
Grade 2	Recommendation: Hold dose until resolved to grade ≤ 1, then maintain dose level
Grade 3	Mandatory: Hold dose until resolved to grade ≤ 1, then reduce dose ↓ 1 dose level

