> 3.0 - 5.0 x ULN	Recommendation: Maintain dose level. Repeat LFTs ^b as soon as possible, preferably within 48-72 hours from awareness of the abnormal results; if abnormal lab values are confirmed upon the repeat test, then monitor LFTs ^b weekly, or more frequently if clinically indicated, until resolved to ≤ 3.0 x ULN
> 5.0 - 10.0 x ULN	Mandatory: Omit dose. Repeat LFTs ^b as soon as possible, preferably within 48-72 hours from awareness of the abnormal results; monitor LFTs ^b weekly, or more frequently if clinically indicated, until resolved to ≤ 3.0 x ULN. Then: If resolved in ≤ 14 days, resume at prior dose level If resolved in > 14 days, resume with reduced dose ↓ 1 dose level
> 10.0 - 20.0 x ULN	Mandatory: Omit dose. Repeat LFTs ^b as soon as possible, preferably within 48-72 hours from awareness of the abnormal results; monitor LFTs ^b weekly, or more frequently if clinically indicated, until resolved to ≤ baseline. Then resume with reduced dose ↓ 1 dose level
> 20.0 x ULN	Mandatory: Permanently discontinue
If elevated at baseline:	
> Baseline - 3.0 x Baseline AND ≤ 5 x ULN	Recommendation: Maintain dose level
> 3.0 x Baseline AND > 5.0 x ULN (duration less than 2 weeks)	Recommendation: Maintain dose level. Repeat LFTs ^b as soon as possible, preferably within 48-72 hours from awareness of the abnormal results; if abnormal lab values are confirmed upon the repeat test, then monitor LFTs ^b weekly, or more frequently if clinically indicated, until resolved to ≤ ULN or baseline
> 3.0 x Baseline AND > 5.0 x ULN (duration more than 2 weeks):	Mandatory: Omit dose. Repeat LFTs ^b as soon as possible, preferably within 48-72 hours from awareness of the abnormal results; if abnormal lab values are confirmed upon the repeat test, then monitor LFTs ^b weekly, or more frequently if clinically indicated, until resolved to ≤ ULN or baseline. If resolved, resume with reduced ↓ 1 dose level.
> 5.0 x Baseline AND > 8.0 x ULN (irrespective of the duration):	Mandatory: Omit dose. Repeat LFTs ^b as soon as possible, preferably within 48-72 hours from awareness of the abnormal results; if abnormal lab values are confirmed upon the repeat test, then monitor LFTs ^b weekly, or more frequently if clinically indicated, until resolved to ≤ ULN or baseline. If resolved, resume with reduced ↓ 1 dose level.
> 20.0 x ULN	Permanently discontinue
Combined ^c elevations of AST or ALT and total bilirubin	

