8.4.2 Laboratory evaluations

Central laboratory will be used for analysis of hematology, biochemistry, coagulation, serum pregnancy and hepatitis marker specimens collected (safety monitoring) as specified in [Table 8-1](#). The time windows granted for laboratory evaluations are identical with the corresponding visit time windows for each visit (see [Section 8](#)).

Additional unscheduled blood draws may be performed at the discretion of the investigator at any time during the study. For example, if the PCR sample was lost during transit or result is difficult to analyze, to confirm a loss of response to study treatment or as clinically indicated.

If the COVID-19 pandemic limits or prevents on-site study visits, if pre-agreed with Novartis and considered by the Investigator it is in the interest of the participant's health to perform study procedures remotely, safety samples that can be collected remotely will be collected and analyzed in line with the study laboratory manual. If participants cannot visit the site for protocol specified safety lab assessments or in case of central lab logistical challenges an alternative laboratory (local) collection site may be used. Please note that BCR-ABL1 quantification must be performed centrally. Where samples are collected and analyzed at a local laboratory instead of the central laboratory, Novartis will ensure the results reported for

hematology and chemistry described below are equivalent to central laboratory collection and analysis by collecting the local normal ranges.

Table 8-5 Central clinical laboratory parameters collection plan

Test category	Test Name
Hematology	Hemoglobin, platelets, red blood cells, white blood cells, WBC morphology with differential (basophils, eosinophils, lymphocytes, monocytes, neutrophils, promyelocytes, myelocytes, metamyelocytes, blast and other)
Chemistry	Albumin, alkaline phosphatase, ALT (SGPT), AST (SGOT), total calcium, total calcium (corrected for albumin), creatinine, creatine kinase, potassium, magnesium, sodium, phosphate (inorganic phosphorus), direct bilirubin, indirect bilirubin, total bilirubin, total cholesterol, LDL cholesterol, HDL cholesterol, total protein, triglycerides, blood urea or Blood Urea Nitrogen (BUN), uric acid, amylase, lipase, serum glucose (fasting), Hemoglobin A1c (at screening only), Creatinine clearance (Cockcroft-Gault formula)
Coagulation	International Normalized Ratio (INR), Activated Partial Thromboplastin Time (aPTT)

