If the event worsens the event should be reported a second time in the CRF noting the start date when the event worsens in toxicity. For grade 3 and 4 adverse events only, if improvement to a lower grade is determined a new entry for this event should be reported in the CRF noting the start date when the event improved from having been Grade 3 or Grade 4.

Conditions that were already present at the time of informed consent should be recorded in medical history of the participant.

Adverse events (including lab abnormalities that constitute AEs) should be described using a diagnosis whenever possible, rather than individual underlying signs and symptoms.

Adverse event monitoring should be continued for at least 30 days following the last dose of study treatment.

Once an adverse event is detected, it must be followed until its resolution or until it is judged to be permanent (e.g. continuing at the end of the study), and assessment must be made at each visit (or more frequently, if necessary) of any changes in severity, the suspected relationship to the interventions required to treat it, and the outcome.

Progression of malignancy (including loss of response, progression to accelerated phase or blast crisis and death due to disease progression) should not be reported as a serious adverse event, except if the investigator considers that progression of malignancy is related to study treatment.

Adverse events separate from the progression of malignancy (i.e. deep vein thrombosis at the time of progression or hemoptysis concurrent with finding of disease progression) will be reported as per usual guidelines used for such events with proper attribution regarding relatedness to the drug.

Information about adverse drug reactions for the investigational drug can be found in the Investigator's Brochure (IB).

Abnormal laboratory values or test results constitute adverse events only if they fulfill at least one of the following criteria:

- they induce clinical signs or symptoms
- they are considered clinically significant
- they require therapy

Clinically significant abnormal laboratory values or test results must be identified through a review of values outside of normal ranges/clinically notable ranges, significant changes from baseline or the previous visit, or values which are considered to be non-typical in participant with the underlying disease.

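### Table 6-4 has no row for an isolated AST/ALT value above 5x ULN but within 3x baseline in patients whose transaminases were raised at entry

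*Protocol*

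**What the plan says.** Protocol Section 6.6.3, Table 6-4, splits the rules for isolated AST or ALT elevation by baseline status. The block for patients with elevated baseline values has five rows:

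1. "> Baseline - 3.0 x Baseline AND ≤ 5 x ULN": maintain dose. No repeat test or monitoring is stated.
2. "> 3.0 x Baseline AND > 5.0 x ULN (duration less than 2 weeks"): maintain dose, repeat liver tests, preferably within 48-72 hours, and monitor weekly if confirmed.
3. "> 3.0 x Baseline AND > 5.0 x ULN (duration more than 2 weeks"): mandatory hold, with repeat and weekly tests, resuming one dose level lower.
4. More than 5x baseline and more than 8x ULN, at any duration: mandatory hold, with the same testing and dose reduction.
5. More than 20x ULN: permanent discontinuation.

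The table also has grade-based rows headed "Non-hematologic adverse reactions except where further specified in individual sections".

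On entry, inclusion criterion 7 (Section 5.1) limits bilirubin, lipase, alkaline phosphatase and creatinine clearance. It sets no limit on AST or ALT. The Amendment 01 summary explains how the block arose: "In addition, appropriate dose modifications guidelines in patients having elevated transaminase levels at baseline are added". The same amendment removed the exclusion for active liver disease, "as it was not in sync with inclusion of patients having baseline moderate hepatic impairment".

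**The concern.** Rows 1 to 4 each join a baseline multiple and a ULN multiple with AND. Row 1 needs the value to be under both of its limits. Rows 2 to 4 need it to be over both of theirs. A value that is over the ULN limit but within the baseline limit belongs to neither group.

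The 5x ULN cap in row 1 takes these values out of the maintain-dose instruction, and no other row receives them. The patients concerned are those for whom the block was written. The uncovered values lie in the 5- to 20-fold range that, according to the amendment summary, a regulator had asked the sponsor to revisit. At stake is consistent safety management: a site looking for the AST/ALT rule finds none, and two sites may act differently on the same result.

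**Working it through.** **Inputs.** The five rows listed above, from Table 6-4. Let b be the baseline and x the on-treatment value, both in multiples of ULN, with b > 1 and x > b. The documents give no distribution of baseline AST/ALT, so the values of b below are assumptions.

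**Which rows can a value with 5 < x ≤ 20 and x ≤ 3b meet?**
- Row 1 needs x ≤ 5. It fails because x > 5.
- Rows 2 and 3 need x > 3b. They fail because x ≤ 3b.
- Row 4 needs x > 5b. It fails because x ≤ 3b < 5b.
- Row 5 needs x > 20. It fails because x ≤ 20.

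No row applies. The uncovered range runs from above 5 up to the smaller of 3b and 20. It exists when 3b > 5, that is b > 5/3 = 1.67. If b is itself above 5, only values above b count as a rise.

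| Assumed baseline (x ULN) | 3 x baseline | Values with no row (x ULN) |
|---|---|---|
| 1.5 | 4.5 | none above 5 |
| 2 | 6 | above 5 to 6 |
| 2.5 | 7.5 | above 5 to 7.5 |
| 3 | 9 | above 5 to 9 |
| 4 | 12 | above 5 to 12 |

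From b = 20/3 = 6.67 upward, the uncovered range reaches 20x ULN.

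**Neighbouring cases.**
- Normal baseline, x = 5.1: mandatory hold (normal-baseline row for above 5 to 10x ULN).
- b = 1.5, x = 5.1: 3b = 4.5, so both limits are crossed. Rows 2 and 3 apply, with a repeat test and, if confirmed, weekly monitoring.
- b = 3, x = 8.5: 3b = 9, so only the ULN limit is crossed. No row applies.
- b = 3, x = 9.1: both limits are crossed and 5b = 15 is not. Rows 2 and 3 apply, with a repeat test and a hold after 2 weeks.

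The instructions therefore go from maintain (up to 5x ULN), to nothing, to repeat and monitor, as one patient's value climbs.

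**Does the combined AST/ALT and bilirubin row help?** For a raised baseline it needs AST/ALT above 3x baseline or above 8x ULN, together with bilirubin above 2x baseline and above 2x ULN. Take b = 3 and ALT at 7x ULN with raised bilirubin. Since 7 is neither above 9 nor above 8, the row is not met. Footnote c of the table then sends the site back to the isolated AST/ALT rows, where 7x ULN has no row.

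**Two smaller wording gaps.** When b < 1.67, values above 3b but at or below 5x ULN also have no row: at b = 1.2, above 3.6 to 5x ULN; at b = 1.5, above 4.5 to 5x ULN. These sit inside the normal-baseline row for above 3 to 5x ULN, which also maintains dose, so mainly the repeat test is missing. In addition, a duration of exactly 2 weeks falls in neither row 2 nor row 3.

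**The case against.** The strongest reply is that the practical harm is narrow. Rows 2 to 4 act only when both a baseline multiple and a ULN multiple are crossed, so a site could reasonably infer that crossing one means maintain dose. Row 1 itself asks for no repeat test. That inference is plausible, but it makes the 5x ULN cap in row 1 pointless, and the table does not state it.

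A second reply is that other provisions catch these patients. The generic non-hematologic rows might be read as the fallback, but they apply except where a section specifies otherwise, and AST/ALT has its own section. They contain no liver-test schedule. The documents do not show how a raised-baseline AST/ALT value would be graded, so which generic action would follow cannot be established. Section 8.4.2 says "Additional unscheduled blood draws may be performed at the discretion of the investigator at any time during the study", and Section 10.1.1 says "Once an adverse event is detected, it must be followed until its resolution or until it is judged to be permanent". Section 9.1.1 obliges the investigator to stop treatment that would harm the patient. These are real protections that depend on judgment, and none sets an AST/ALT-specific action.

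Third, entry controls narrow the population: exclusion 6 (severe or uncontrolled disease) and the hepatitis B and C exclusions remain. They do not bar a baseline above 1.67x ULN.

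A reader might infer more than this. The documents do not support saying that:
- affected patients go unmonitored. Scheduled chemistry continues, and 12 weeks is the longest scheduled interval after Week 12, not the expected delay;
- dosing on up to 3x baseline is wrong in itself. That is a clinical choice open to the sponsor.

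**Conclusion.** The gap is real and follows from the table's wording alone: an isolated AST/ALT value above 5x ULN but within 3x baseline has no row up to 20x ULN once baseline exceeds 1.67x ULN. It should be corrected, because the table gives a firmer instruction for 5.1x ULN from a baseline of 1.5x ULN than for 8.5x ULN from a baseline of 3x ULN.

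The width of the gap depends on the assumed baseline. How many enrolled patients have such baselines is unknown. The point concerns consistent safety management only. It does not touch the week 48 MMR endpoint, the sample size or the primary test.

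**What to change.** Leave row 1 as it is and add one row to the elevated-baseline block:

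- **Range:** above baseline, above 5.0x ULN and up to 20.0x ULN, but not more than 3.0x baseline.
- **Action:** maintain dose; repeat liver tests, preferably within 48-72 hours; if confirmed, test weekly or more often as clinically needed until the value is back to ULN or baseline.
- **Persistence:** the sponsor's safety team should decide, and the row should state, whether a hold applies if the value lasts beyond 2 weeks. This is a clinical decision that the documents do not settle.

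The above-baseline condition matters. Without it, a patient who improves from 6x to 5.5x ULN would trigger the row.

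As minor wording, make row 3 start at 2 weeks or more, and give values above 3.0x baseline but at or below 5.0x ULN the same repeat-and-monitor instruction with dose maintained.

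The cost is table wording in an amendment and a few extra liver tests in patients with raised baseline values.
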